27.4 Alternative methods

The analyses outlined in the previous sections should be considered as intentions in the sense that they rely on different assumptions. These assumptions may of course be challenged by the data, and the analyses will have to resort to other

models. Alternatives may include Box-Cox analysis/transformation to achieve normality for non-normal continuous variables, bootstrapping random effects, and generalized additive mixed models (GAMM) as an alternative to the generalized linear mixed models.

27.5 Sensitivity analyses

We intend to assess the robustness of the results by

- Repeating the primary analysis in the PPP.
- Analyze the primary outcome using multiple imputation (MI) (see 28.3).
- Repeating the primary ITT analysis by including each of the following baseline variables as a covariate:
 - o study centre (the stratification variable)
 - o previous NSAID use (yes/no)
 - o imaging findings

27.6 Subgroup analysis

We will not analyze subgroups.

28 Missing data

28.1 Measures to minimize the amount of missing data

- To facilitate simple access and timely responses patients receive daily text message reminders with a link to the electronic diary. A paper CRF is provided as back-up in case the eCRF is unavailable.
- To ensure clear and concise wording, and response alternatives, only validated patient reported outcomes, appropriate for sciatica, are used.
- To reduce unnecessary response burden the number of outcomes are limited.
- To ensure data completeness study staff checks the e-CRF at day 2 and day 5, and if necessary contacts the patient to clear up issues that may impair compliance.
- To preserve the ITT population data will be continued to be collected after withdrawal. Reasons for withdrawal are pre-specified.

28.2 Assessments of missing data

The number, timing, pattern, and known reasons for missing values will be assessed and summarized by treatment group and examined according to baseline characteristics. Missing data will be considered as either missing completely at random (MCAR), missing at random (MAR) or missing not at random (MNAR). If unexpected missing data patterns are found, sensitivity analyses in addition to those specified in 27.6, may be performed.

28.3 Statistical methods to handle missing data

The LMM and GLMM statistical models for analysis of the primary outcome and continuous secondary outcomes assume that missing data follow a missing at random (MAR) pattern, in which the probability of missingness may depend on other observed outcome values in the model, but are not related to the unobserved values of missing responses themselves. For outcomes not analyzed using likelihood-based methods (LMM and GLMM) missing data will be handled using multiple imputation (MI). MI will also be used in sensitivity analyses, see above (27.6).

MI under MAR or MCAR will initially be performed separately within each treatment arm. The models will include all variables in the analytic models plus the values of all baseline characteristics reported in Table 1. A total of 50 imputed data sets will be created. Pooled estimates will be calculated using Rubin's rules.

29 Additional analyses

29.1 Assessment of patient blinding.

At the end of treatment (day 10), or withdrawal, patients are asked to guess what treatment they have received. The response categories include (i) Naproxen, (ii) placebo and (iii) don't know. Descriptive data (2x3 table) will be presented, no statistical analyses will be performed.

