# **9 STATISTICAL METHODS AND DATA ANALYSIS**

## **9.1 DETERMINATION OF SAMPLE SIZE**

The sample size calculation is based on a mean difference between the Naproxen group and the placebo group of 1.5 (0-10) at ten days with a SD of 2.5 using a two-sample t test. There is no robust evidence for the smallest worthwhile

between group pain relieving effect in sciatica. In previous sciatica studies sample size were calculated based on between group differences of 1.5 and 1.0 [80, 81]. In a recent RCT of pregabalin the sample size was calculated based on a between group difference of 1.5 [36]. In knee osteoarthritis, a condition in which NSAIDs are generally recommended, the treatment effect of NSAIDs is about 1.0 [82-84]. The estimated SD of 2,5 is based on a recent Cochrane review of NSAID studies in sciatica [30].

Assuming 90% power and a two-tailed 5% significance level a sample size of 60 subjects is needed in each treatment arm. Allowing for a combined dropout and non-compliance rate  $\leq 20\%$  [85] the total number of subjects will be 150.

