8.2 Secondary objectives

To demonstrate that, in patients with sciatica, treatment with Naproxen 500 mg twice daily is superior to placebo with respect to

- improvement in back pain intensity
- improvement in disability
- use of rescue medication
- global perceived change in sciatica/back problem
- improvement in sciatica symptom bothersomeness
- 30% and 50% improvement in leg pain
- concomitant use of opioid analgesics
- ability to work and study

STUDY METHODS

9 Trial Design

NIS is a multicenter, two-armed randomized, placebo controlled, double blind, parallel group, superiority phase IV trial.

10 Randomization

Study medicines will be packaged and labelled according to a pre-generated random number sequence; each sealed box will have a unique participant number. Computer-generated block randomization, stratified by center, will be used. Allocation to Naproxen or placebo will be at a 1:1 ratio.

11 Sample size

The sample size estimation is based on a minimum difference of interest between the Naproxen group and the placebo group of 1.5 at day 10. Assuming a standard deviation SD of 2.5 (see protocol for details and references), 90% power and a two-tailed 5% significance level, 60 subjects in each treatment arm is required. Allowing for a combined dropout and non-compliance rate $\leq 20\%$ a sample size of 150 was determined.

12 Framework

Analyses will be within a superiority hypothesis testing framework, comparing Naproxen to placebo.

13 Interim analyses and stopping guidance

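### The only prespecified missing-data sensitivity analysis for leg pain makes the same kind of MAR assumption as the primary model, and no MNAR analysis is specified

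*SAP*

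**What the plan says.** SAP 27.1 analyses daily leg pain with a linear or generalized linear mixed model. SAP 28.3 states that these models "assume that missing data follow a missing at random (MAR) pattern".

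SAP 27.5 lists three kinds of robustness check: a per-protocol repeat, multiple imputation (MI) of leg pain ("Analyze the primary outcome using multiple imputation (MI) (see 28.3"), and adding centre, previous NSAID use or imaging findings as a covariate. Only MI addresses missing data. SAP 28.3 defines it: "MI under MAR or MCAR will initially be performed separately within each treatment arm". The imputation model holds the analysis variables "plus the values of all baseline characteristics reported in Table 1". There are 50 imputed data sets, pooled by Rubin's rules.

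SAP 19.1 and 28.2 provide for classing missing data as MCAR, MAR or MNAR, but no listed analysis uses the MNAR class. SAP 28.2 and 29.2 allow extra sensitivity analyses if unexpected patterns appear, without naming a method or saying what counts as unexpected. The word *initially* in 28.3 is followed by no later step. SAP 28.2 and 28.3 both point to 27.6 for the sensitivity analyses, but 27.6 is the subgroup section; the list is in 27.5. Protocol 9.5.1 leaves the missing-value strategy to the blind review.

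**The concern.** A sensitivity analysis for missing data should vary the assumption that the data cannot check. Here the primary model and its check both assume that, given what was observed, missing scores behave like observed ones. If patients stop their diaries because of unrecorded worsening or intolerance, both analyses can be wrong in the same direction and by about the same amount. Planned Table 8 would then show two similar estimates, and a reader would take that as robustness.

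Such dropout is foreseeable in a 10-day pain trial with daily self-report, so a clause that applies only to unexpected patterns may never be used. If it is used, the method would be chosen after missingness has been summarised by group.

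**Working it through.** **1. The plan's own figure.** Inputs: "minimum difference of interest between the Naproxen group and the placebo group of 1.5 at day 10" (SAP 11), "with a SD of 2.5 using a two-sample t test" (Protocol 9.1), "Assuming 90% power and a two-tailed 5% significance level a sample size of 60 subjects is needed in each treatment arm" (Protocol 9.1) and "Allocation to Naproxen or placebo will be at a 1:1 ratio" (SAP 10).

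n per arm = 2 × (1.960 + 1.282)² × 2.5² / 1.5² = 58.4, so 59 by the normal approximation. The exact t calculation gives power 0.898 at 59 and 0.903 at 60, hence 60. Then 120 / (1 − 0.20) = 150, or 75 per arm. The sample size reproduces and is not in question; it supplies the standard error used below.

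**2. Standard error.** SE = 2.5 × √(2/60) = 0.456. Two-sided 5% margin: 1.96 × SE = 0.895.

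**3. Effect of a departure from MAR.** Suppose a fraction f of one arm is missing at day 10 and those patients' true mean is δ points worse than MAR imputes. That arm's mean, and so the difference, moves by f × δ. For δ = 2: 0.10 × 2 = 0.2 and 0.20 × 2 = 0.4 points.

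**4. Shift at which significance is lost.** With δ applied to naproxen only, δ* = (MAR estimate − 0.895) / f.

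| MAR estimate (points in favour of naproxen) | f = 10% | f = 20% |
|---|---|---|
| 1.0 | 0.105/0.10 = 1.1 | 0.105/0.20 = 0.5 |
| 1.2 | 0.305/0.10 = 3.1 | 0.305/0.20 = 1.5 |
| 1.5 | 0.605/0.10 = 6.1 | 0.605/0.20 = 3.0 |

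The lower estimates are not remote: Protocol 9.1 cites an NSAID effect of about 1.0 in knee osteoarthritis. A baseline-adjusted model may be more precise. With SE 0.391, the average from a reduced imputation model in simulation at 20% missing, the margin is 0.766 and the 20% column becomes 1.2, 2.2 and 3.7.

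**5. Do two MAR analyses expose the problem?** Simulation: 75 per arm, 20% missing in each arm, naproxen patients with worse day-10 pain more likely to drop out, 300 replicates, 30 imputations. The reduced MAR imputation stands in for the primary model.

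| Analysis | Mean estimate |
|---|---|
| Complete data | −1.51 |
| Reduced imputation under MAR | −1.88 |
| SAP-style by-arm imputation under MAR | −1.90 |
| Reduced imputation, +2 points in naproxen | −1.48 |

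The two MAR analyses agree to 0.02 and share a bias of about 0.4. The delta-adjusted one does not share it. When dropout was unrelated to pain, the same +2 shift moved the estimate from −1.48 to −1.08, which is the 0.4 of step 3.

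**The case against.** **Missingness may be small.** The 20% allowance combines dropout with non-compliance, and non-compliant patients can still report pain. Collection continues after withdrawal (SAP 28.1) and after stopping trial drug alone (Protocol 6.4.1), with daily reminders and coordinator entry by telephone (Protocol 8.1.1). All of this stands: 20% is a ceiling, and a reader should not infer that the plan expects only 60 patients per arm with complete scores. It does not remove the gap. Diaries open for only 24 hours on the scheduled date (SAP 15), and patients may be discontinued from assessments (Protocol 6.3).

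**The bias may be smaller.** Informative dropout in both arms would partly cancel, and late dropout affects only some days of an effect estimated over the treatment period (SAP 27.1). At the design effect of 1.5 the shift needed is large. These points stand, and a tipping-point analysis would show them.

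**The imputation is not identical to the primary model.** Its auxiliary variables widen the MAR condition, so it can differ where dropout depends on them. A reader might infer that it will report robustness however large the bias is; that goes too far. Nor should its inability to test MAR be held against it specifically: no analysis of observed data can do that, including the one proposed here.

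**The imputation model may look too large for the trial.** It has about 33 to 35 predictors per daily score for 60 to 75 patients per arm. In simulations with data missing at random it could be fitted, was unbiased and had 94 to 98% coverage. Its average SE exceeded that of a reduced model pooled across arms by 5%, 10% and 21% at 5%, 11% and 20% missing. The true loss of precision at 20% was smaller: empirical SE 0.432 against 0.426 in one simulation and 0.419 against 0.386 in another. That supports an efficiency preference and no more.

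**Conclusion.** The point holds as a gap in prespecification. The SAP's only missing-data check on the primary outcome stays within MAR, its MNAR class leads to no analysis, and its optional analyses have neither method nor trigger. Agreement between the two planned analyses would not be evidence about departures from MAR.

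The consequence is conditional. A 2-point shift in one arm moves the day-10 difference by 0.2 to 0.4 points at 10 to 20% missing. That could change the conclusion if the estimate is near 1.0 to 1.2, and is unlikely to if it is 1.5 or more. The missing rate, the shift, its confinement to one arm and the simulated mechanism are assumptions; the documents give none of them. They do not support a claim that the primary result will be biased. The change should be made before the data are analysed, but the primary analysis itself need not change.

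**What to change.** In SAP 27.5 and 28.3:

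- Prespecify a delta-adjusted MI of leg pain. Impute under MAR, add 0.5, 1, 1.5 and 2 points to imputed scores, continue upward until the conclusion changes, and refit the primary model each time. State whether the shift applies to all imputed days and how values above 10 are handled.
- Shift one arm at a time, coded arm A and then B, so that the analyst stays blind. An equal shift in both arms moves the difference only by delta times the difference in missing fractions, which is near zero when missingness is balanced.
- Report the tipping delta and whether it is plausible. Run the analysis whatever class the missing data are given.
- Correct the references to 27.6 in 28.2 and 28.3 so that they point to 27.5.

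Optionally, limit the imputation model to daily and baseline leg pain, age, sex and a few stated predictors of dropout.

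Cost: SAP wording and a few more runs of an imputation already planned. No new data and no change to the sample size.

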13.2 Early stopping

The safety profile of Naproxen is well documented and established, and the dosing is under its approved label use. There is no reason to expect Naproxen to affect the rate of serious sciatica complications such as lower extremity paresis or cauda equina syndrome. As Naproxen is used under its approved label use no interim safety analyses will be conducted.

14 Timing of final analysis

All outcomes will be analyzed jointly after the end of the trial, i.e. after the last visit of the last subject, and data locking.

15 Timing of outcome assessments

Primary outcome: Leg pain (the primary outcome) is measured daily from baseline (day 0) to end of treatment (day 10).

Secondary outcomes

- Back pain is measured like leg pain
- Disability, assessed by the Roland Morris Disability Questionnaire for Sciatica (RMDQ-S), is measured at day 0, 5 and 10
- Rescue medication consumption is measured (i) at the end-of study-visit (by pill count) and (ii) daily from day 1 to day 10 (by self-report).
- Global perceived change is measured at day 5 and 10.
- Sciatica bothersomeness, assessed by the Sciatica Bothersomeness Index (SBI), is measured at day 0, 5 and 10.
- Concomitant use of opioid analgesics is assessed on day 0, 5 and 12 (± 2).
- The ability to work or study is measured at day 0 and 10.

Table 1. Timing of outcome assessments

	Baseline	Start of treatment				End of treatment	End of study
–							

Day	0	1	2-4	5 (± 1)	6-9	10	12 (± 2)
	Visit	Home	Home	Home	Home	Home	Visit
-Leg pain -Back pain	X	X	X	X	X	X	X
-SBI -RMDQ-S	X			X		X	X
Global perceived change				X		X	X
Work/study	X					X	X
Rescue medication (pill count)							X
Rescue medication (self-report)		X	X	X	X	X	
Opiod use	X			X			X

SBI Sciatica Bothersomeness Index, RMDQ-S Roland Morris Disability Questionnaire for Sciatica.

Visit windows.

Patient reported outcomes are captured using a web based real-time electronic diary (ViedocMe). The questionnaires are available 24 hours on the scheduled date. The end of study visit is scheduled on day 12 (± 2).

STATISTICAL PRINCIPLES

16 Level of statistical significance

A two-tailed p value of less than 0.05 is considered to indicate statistical significance. We will report nominal p values.

17 Adjustment for multiplicity

We will not adjust for multiple comparisons. This trial has one primary outcome which will be analyzed in a single mixed-effect model and there are no planned subgroup analyses.

18 Confidence intervals

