Demographic and clinical characteristics will be summarised by assigned treatment group without comparisons, as shown in 32.1 (Planned table 1). Categorical variables will be summarised by frequencies and percentages. Percentages will be calculated according to the number of patients for whom data are available. Where values are missing, the denominator, which will be less than the number of patients assigned to the treatment group, will be reported either in the body or a footnote in the summary table. Continuous variables will be summarised by mean and standard deviation, or by medians and interquartile range (IQR).

ANALYSIS

26 Outcome definitions

26.1 Specification of outcomes.

The primary outcome is leg pain intensity (24 hours average), rated on a 0-10 NRS. Higher scores indicate more severe pain.

Secondary outcomes:

- Back pain intensity (24 hours average), rated on a 0-10 NRS.
- Disability, measured by RMDQ-S (0-23), higher scores indicate worse disability.
- Sciatica bothersomeness, measured by the SBI (0-24), higher scores indicate more symptom bothersomeness.
- $\geq 30\%$ improvement in leg pain score
- $\geq 50\%$ improvement in leg pain score
- Global perceived change measured on a 7-point Likert scale (sciatica/back problem completely gone, much better, better, a little better, no change, a little worse, worse and much worse).
- Rescue medication consumption, measured by pill count, i.e. the number of Paracetamol pills not returned at the end of study. If the Paracetamol package is not returned, self-report data from the electronic diary will be used. Higher rescue consumption indicates more pain.
- Concomitant use of opioids, higher consumption indicate more pain
- Ability to work or study full time, measured by 3 nominal categories (unable, able, other)

We consider the secondary outcomes to have equal importance.

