27.2 Analysis of secondary outcomes

- Back pain intensity will be analyzed using the same model used to analyze the primary outcome.
- Disability and sciatica bothersomeness will be analyzed using the same model used to analyze the primary outcome, but with 3 time points.
- Responder analyses, i.e. 30% and 50% improvement in leg pain intensity, will be performed using a mixed effects logistic regression model to obtain estimates of odds ratios (OR) and 95% CI. Based on the absolute risk reduction (ARR) between Naproxen and placebo we will calculate the numbers needed to treat (NNT) with 95% CI (NNT = 1/ARR).
- Rescue medication consumption and concomitant use of opioids during the treatment period will be analyzed using a suitable regression.
- Work/Study is an unordered categorical variable. The appropriate model is therefore a multinomial with repeated measurements and it will be analyzed using a GLMM.
- Global perceived change is an ordered categorical variable with repeated measurements and will be analyzed using a GLMM.

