27.3 Adjustment for covariates

The statistical analyses of primary and secondary efficacy outcomes will be adjusted for baseline measures of the outcome where one is available [5]. The analysis of rescue medication consumption and use of concomitant opioids will be adjusted for baseline leg or back pain intensity depending on which is worse.

Study center (stratification variable) will not be included as covariate as we expect the majority of participants to be included at one center (Østfold). We will perform a sensitivity analysis with and without adjusting for center. Provided that a sufficient number of patients are included from at least 4 centers, these can be treated as additional random effects in the model.

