32.1 Planned tables

- Table 1. Baseline characteristics of participants by treatment group
- Table 2. Intervention effect on primary and secondary outcomes
- Table 3. Important and not important protocol deviations by treatment group
- Table 4. Baseline concomitant medications by treatment group
- Table 5. Response to blinding question at day 10
- Table 6. Global perceived change (including all response categories) at day 5 and day 10 by treatment group
- Table 7. Adverse events by treatment group and severity (mild / moderate / severe)
- Table 8. Results of sensitivity analyses

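### Rescue and opioid totals that are still missing may be imputed from arm and baseline alone, which can bias these two secondary comparisons if pain-linked loss differs between arms

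*SAP*

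**What the plan says.** - **Analysis model.** SAP 27.2: "Rescue medication consumption and concomitant use of opioids during the treatment period will be analyzed using a suitable regression". No model class is named. Under SAP 27.3 the analysis "will be adjusted for baseline leg or back pain intensity depending on which is worse", and that is the only covariate specified for these two outcomes.
- **When imputation is the main method.** SAP 28.3: "For outcomes not analyzed using likelihood-based methods (LMM and GLMM) missing data will be handled using multiple imputation (MI").
- **Contents of the imputation model.** SAP 28.3: "The models will include all variables in the analytic models plus the values of all baseline characteristics reported in Table 1", and "MI under MAR or MCAR will initially be performed separately within each treatment arm". SAP 32.1 names the table as "Table 1. Baseline characteristics of participants by treatment group". Its suggested design lists baseline items only, among them baseline use of weak and strong opioids.
- **Fallback for rescue.** SAP 26.1: "If the Paracetamol package is not returned, self-report data from the electronic diary will be used". The SAP does not say how a diary with missing days is totalled, and it gives no fallback for opioids.
- **On-study data.** Leg pain is recorded daily. SAP 15 has rescue intake recorded "daily from day 1 to day 10 (by self-report"). SAP 15 places opioid assessment on days 0, 5 and 12, whereas protocol 5.3 and 6.5.5 have other pain medication recorded every day.

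**The concern.** Rescue and opioid use enter the analysis as one total per patient. If the regression is an ordinary one, multiple imputation is the principal missing-data method for them and not a sensitivity check. Read outcome by outcome, the variable list in SAP 28.3 then contains nothing measured after baseline. Take two patients in the same arm with the same baseline, one reporting leg pain of 9 on days 1 to 5 and the other 2, both lost afterwards with no usable total. Their totals would be drawn from the same distribution.

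Missingness must then be random given arm and baseline alone. The mixed model for leg pain asks less, because it conditions on each patient's observed scores. SAP 26.1 itself says that higher rescue and opioid consumption indicates more pain, so on-study pain is an obvious predictor to leave out. If high-pain patients are lost more often on placebo, their likely high intake is replaced by more typical values and the naproxen benefit is understated. If the imbalance runs the other way, it is overstated. The multiple-imputation sensitivity analysis in SAP 27.5 covers the primary outcome only, so it would not reveal this.

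**Working it through.** **Figures from the plan.** The documents give no figure on this point. The arm size and the upper limit for loss come from the sample size section, which reproduces. With a difference of 1.5, SD 2.5, two-sided 5% and 90% power, the exact t test needs 60 per arm (power 0.903), and 120/(1 - 0.20) = 150, or 75 per arm.

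**How the bias arises.** In each arm let q be the proportion of totals that are imputed and g the shortfall of the mean imputed total below the mean true total among those patients. The arm mean is then off by -q x g, so

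bias in (naproxen - placebo) = q_P x g_P - q_N x g_N.

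This is zero when q and g are the same in both arms. A positive value shrinks a negative (beneficial) difference.

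**Assumed inputs, none in the documents.** SD of the total 18 tablets; true difference 4 tablets; correlation of baseline with on-study pain 0.5; correlation of on-study pain with intake 0.3, 0.5 or 0.7; log-odds of loss rising 1.5 per SD of on-study pain. The highest loss, 20%, is borrowed from the plan's combined dropout and non-compliance allowance.

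**Results: large-sample simulation, imputation within arm.**

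| Missing, naproxen / placebo | Correlation of pain with intake | Shrinkage, baseline-only (tablets) |
|---|---|---|
| 10% / 10% | 0.3 to 0.7 | 0.04 or less |
| 2% / 5% | 0.3 to 0.7 | about 0.15-0.4 |
| 5/15, 10/20 or 5/20% | 0.3 | 0.44-0.72 |
| same | 0.5 | 0.76-1.18 |
| same | 0.7 | 1.05-1.61 |

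With on-study pain added to the imputation model, the bias was at most 0.04 tablets throughout.

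**Scale.** SE of the difference = 18 x sqrt(2/75) = 18 x 0.163 = 2.9 tablets. The bias is therefore 0.15/2.9 = 0.05 to 0.4/2.9 = 0.14 SE at 2/5% loss, and 0.44/2.9 = 0.15 to 1.61/2.9 = 0.55 SE at the larger imbalances.

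**Second check, in SD units.** Here the log-odds slope is 1 per SD and the drug effect on pain is 1.5/2.5 = 0.6 SD. At a correlation of 0.5, baseline-only bias was 0.00 when loss was completely random, and 0.00 when slope and rate (20%) were equal in both arms. It was 0.03 with 15% lost on naproxen and 25% on placebo, and 0.07 with 20% lost in each arm but pain-linked on placebo only. In the extreme case where naproxen loses low-pain and placebo high-pain patients, 20% each, it was 0.13 (0.08 to 0.19 for correlations of 0.3 to 0.7). Adding on-study pain gave 0.00 in every case. The placebo-only result shows the mechanism: 0.066/0.20 = 0.33 SD shortfall per imputed patient, or 0.33 x 18 = 5.9 tablets.

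**At trial size.** With 75 per arm, baseline-only imputation shrank the difference by about 0.4-1.1 tablets at 5/15% or 10/20% loss. Adding one on-study pain summary removed the bias and raised the empirical SD of the estimate by at most about 2%.

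No calculation was done for opioids, because the documents give nothing on which to base a scale.

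**The case against.** Four objections carry weight.

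1. **Rescue diaries are not ignored.** A reader might infer that the plan discards daily tablet records. It does not: the diary replaces an unreturned package before any imputation. Pill boxes are also collected at the withdrawal visit, and data collection continues after withdrawal (SAP 28.1). Few rescue totals may reach imputation. What stands is the partly filled diary, for which no rule is given, and opioids, for which no fallback is written.
2. **Pain-linked loss is not enough.** A reader might infer that such loss biases both comparisons. The results above show about zero bias when loss is alike in both arms, and for opioids nothing was computed.
3. **The reading is not forced.** The unnamed regression could be a generalised linear mixed model, and the plural reference to analytic models could mean one joint model containing daily pain. The SAP settles neither. That leaves the complaint conditional, but it is also a reason to amend.
4. **The larger figures are generous.** The 20% allowance includes non-compliers, who need not have missing totals. If all of Table 1 predicted on-study pain at 0.7 instead of 0.5, the bias at the larger imbalances would fall from 0.44-1.62 to 0.33-1.16 tablets.

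Dropping Table 1 from the imputation model altogether would be a mistake, since it holds baseline opioid use.

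**Conclusion.** The point holds in conditional form. If the regression is not a mixed model, totals that remain missing are imputed under an assumption that ignores on-study pain and partial intake. The comparison can then be biased, in either direction, when pain-linked loss differs between arms. The plausible size for rescue runs from about zero to 1.6 tablets, at most about half a standard error, and it rests on assumed SD, effect, correlations and loss rates. The documents do not support a claim that bias will occur, or any figure for opioids. Only secondary outcomes are affected; the primary result and the sample size are not. The change is worth making because the remedy is cheap and removed the bias in every scenario examined.

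**What to change.** Amend the SAP as follows.

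- **27.2:** name the regression for the rescue and opioid totals, so that it is clear whether imputation applies.
- **28.3:** for these totals, add as auxiliary variables a low-dimensional summary of observed on-study leg pain (for example the mean of the recorded daily scores) and the observed partial intake (for example mean tablets per recorded day, and day 5 opioid use). Alternatively, impute missing days and sum. Keep the analysis covariates and baseline opioid and pain-medication use. Trim other Table 1 terms only if the within-arm models prove unstable.
- **26.1:** state that missing days in a partly filled diary are handled this way and are not counted as zero.
- **15, with protocol 5.3 and 6.5.5:** reconcile the opioid recording schedule (days 0, 5 and 12 against daily), since it decides which partial opioid data exist.

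The cost is SAP wording, slightly more programming and a slightly larger imputation model. Daily leg pain, daily tablet counts and day 5 opioid use are already scheduled, so no extra patients or visits are needed.
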